1.2.2 Clinical Pharmacokinetics of Vemurafenib

Pharmacokinetic (PK) information is available for patients treated with 160 to 1120 mg twice daily (bid) of the optimized clinical formulation (also referred to as the micro-precipitated bulk powder [MBP] formulation). The MBP formulation has been provided as 40-mg capsules (dry granulation method), 80 mg capsules (wet granulation method), and 120-mg capsules (roller compaction method) in the PLX06-02 Phase I trial, a dose-escalation study in patients with metastatic melanoma.

The vemurafenib MBP formulations were developed to increase bioavailability. Dose-proportional increases were seen in exposure with the 40-, 80-, and 120-mg capsules, particularly from 240 to 960 mg bid. There were some patients who were high and low exposure outliers. The reason for this variability is currently unknown.

Steady-state exposure is expected to be reached by 15 days and mean steady-state levels of vemurafenib (area under the concentration–time curve [AUC_{0–24h}]) ranged from 428 µM·h to 1800 µM·h in the PLX06-02 Phase I trial. The 960 mg bid dose of vemurafenib achieved mean steady-state exposures of 90 µM and 1800 µM·h for maximum plasma concentration (C_{max}) and AUC_{0–24h}, respectively. The mean effective half-life of vemurafenib across all dose cohorts was ~50 hours (range of 30–80 hours).

Mean steady-state vemurafenib exposures (C_{max} and AUC_{0–8h}) achieved with the to-be-marketed 240-mg tablet formulation in the Phase II study, NP22657 (n=60), were found to be 11% higher compared with the 120-mg capsule formulation (PLX06-02, n=30) in metastatic melanoma patients dosed with 960 mg bid.

Additional information can be obtained from the vemurafenib IB.

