3.5 Rationale for Pharmacokinetic Evaluation Schedule

Vemurafenib and cobimetinib will be used in combination in metastatic melanoma patients for the first time in this study.

Historical PK data are available for both compounds as monotherapies. Data from the combination of both drugs used in this study will be compared with these historical controls to monitor any unexpected changes in pharmacokinetics that may occur following the co-administration of both drugs. Currently, no major concerns have been identified for any PK interaction between vemurafenib and cobimetinib. In vitro experiments indicate that vemurafenib may be a weak substrate and moderate inhibitor of Pgp. Cobimetinib is a substrate of Pgp and combination therapy with vemurafenib may lead to an alteration of plasma exposures of cobimetinib. Additional nonclinical and clinical data regarding the metabolism of vemurafenib suggest that the drug may be a mild inducer of CYP3A4. Preliminary information suggests that CYP3A and UGT2B7 are the enzymes responsible for cobimetinib metabolism. However, the fraction of cobimetinib metabolized by CYP3A is unknown. Thus, induction of CYP3A4 by vemurafenib may lead to decreased systemic exposures of cobimetinib.

In vitro CYP inhibition studies suggest that cobimetinib has a moderate potential to interact with drugs that are substrates for CYP2D6 (IC_{50} 1.8 μ M) or CYP3A (IC_{50} 5.9–1.7 μ M; K_i 7.6 μ M). It is unclear how cobimetinib may alter the pharmacokinetics of vemurafenib.

For patients who have progressed while receiving vemurafenib monotherapy immediately preceding enrollment in this trial only, an exposure time profile for vemurafenib will be taken at Day -1, spanning an 8-hour post-dose period to determine the exposure level of this drug prior to study start. Patients assigned to Cohorts 1, 1A, 2, 2A, and 1C who tolerated 960 mg bid vemurafenib prestudy will be dose reduced to 720 mg bid for at least 1 week prior to study start.

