 - Serum creatinine \leq 1.5 X ULN or creatinine clearance \geq 50 ml/min on the basis of measured creatinine clearance from a 24-hour urine collection or the Cockcroft-Gault glomerular filtration rate estimation: $(140 - \text{age}) \times (\text{weight in kg}) \times (0.85 \text{ if female})$
 1. $72 \times$ (serum creatinine in mg/dL)
10. INR and aPTT \leq 1.5 X ULN
11. Female patients of childbearing potential and male patients with partners of childbearing potential must agree to always use an effective form(s) of contraception during the course of this study and for at least 6 months after completion of study therapy.
 - Females of childbearing potential are defined as sexually mature women without prior hysterectomy who have had any evidence of menses in the past 12 months. In order to be considered NOT of childbearing potential, amenorrhea for a period of 12 months or longer must have occurred in the absence of chemotherapy, anti-estrogens, or ovarian suppression.
 - Effective forms of contraception includes surgical sterilization, a reliable barrier method with spermicide, birth control pills, or contraceptive hormone implants
12. Negative serum pregnancy test within 7 days prior to commencement of dosing in women of childbearing potential; women of non-childbearing potential may be included if they are either surgically sterile or have been naturally menopausal

- for ≥ 1 year. Women of non-childbearing potential need not undergo the pregnancy test.
13. Absence of any psychological, familial, sociological, or geographical condition potentially hampering compliance with the study protocol and follow-up schedule; those conditions should be discussed with the patient before trial entry.
 14. Consent to provide archival tissue (either a paraffin-embedded tissue block or up to 15 unstained slides) for molecular analyses to investigate BRAF, CRAS, CRAF, PTEN, RAS, and MEK, as well as other pathway markers on the protein, epigenetic, and genetic level. See [Table 9](#) for details.
 15. Consent to undergo tumor biopsies of accessible lesions for PD biomarker and molecular analyses including BRAF, CRAF, PTEN, RAS, and MEK, as well as other pathway markers on the protein, mRNA, and genetic level. See [Table 9](#) for details.

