4.4.3 Medication Precautions in Case of Drug–Drug Interactions

Vemurafenib:

On the basis of nonclinical data, vemurafenib may have the potential to cause DDI with concomitant medications that are primarily eliminated by CYP2C9. Patients should be advised to consult with their physician before taking any of the listed medications:

- Non-steroidal anti-inflammatory drugs (e.g., ibuprofen, diclofenac, meloxicam)
- Oral hypoglycemic agents (e.g., tolbutamide, glipizide, glyburide, glimepiride)
- Antihypertensives (e.g., losartan, irbesartan, torsemide)
- Anticonvulsants (e.g., phenytoin)
- Anticoagulants (e.g., warfarin)
- Lipid-lowering drugs (e.g., fluvostatin)

In a CYP450 in vivo metabolism study (NP22676), vemurafenib inhibited CYP1A2 and induced CYP3A4 activity in melanoma patients by approximately 3-fold and 2-fold, respectively. If CYP1A2 substrates must be co-administered with vemurafenib, investigators should assess the safety risk associated with a potential increase in plasma

concentrations of CYP1A2 metabolized drugs. If CYP3A4 substrates must be co-administered with vemurafenib, investigators should monitor the signs of reduced benefit of CYP3A4 metabolized drugs due to a potential decrease in their plasma concentration. Doses of concomitant CYP1A2 and CYP3A4 drugs, but not the dose of vemurafenib, may be adjusted as necessary to alleviate the impact of drug interaction.

For CYP2C9, data suggested that the relatively strong nonclinical signal inhibition, ($IC_{50}=5.9 \mu\text{M}$ in vitro in hepatic microsomes) did not translate to a DDI with this CYP450 isoform. However, vemurafenib was associated with a decrease in clearance of warfarin from plasma, and a 19% increase in the mean exposure (AUC) that did not fall outside of the equivalence boundary.

Little metabolism of vemurafenib (< 10%) was detected in nonclinical studies and in data from a human mass balance study with ^{14}C - vemurafenib in patients with melanoma (Study NP25158). Nonclinical studies suggest that CYP3A4 metabolism and subsequent glucuronidation are responsible for the metabolism of vemurafenib. No clinical data are currently available evaluating the effects of CYP3A4 inducers or inhibitors on vemurafenib exposure.

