[Appendix 10](#) includes a non-exhaustive list of typical examples of CYP1A2, CYP3A4, and CYP2C9 substrates and CYP3A4 inducers and inhibitors. A more extensive list of medications can be found online at the following link: <http://medicine.iupui.edu/clinpharm/ddis/Table.asp>. For further information see the Investigator's Brochure.

Cobimetinib:

On the basis of in vitro data showing that cobimetinib is metabolized by the hepatic cytochrome CYP3A4, the drugs listed below should be avoided. If use of one of these drugs is necessary, the risks and benefits and potential alternatives should be discussed with the Medical Monitor prior to its concomitant use with cobimetinib.

- Strong CYP3A4/5 inhibitors such as, but not limited to, atazanavir, clarithromycin, indinavir, itraconazole, ketoconazole, nefazodone, nelfinavir, ritonavir, saquinavir, telithromycin, troleandomycin, and voriconazole
- Strong CYP3A4/5 inducers such as, but not limited to, rifampin, carbamazepine, rifampentine, phenytoin, and Phenobarbital

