Appendix 10: Impact of Vemurafenib on Concomitant Medications

Impact of RO5185426 on Concomitant Medications		
Substrates		
CYP 1A2 ¹	CYP 2C9 ¹	CYP3A4 ²
amitriptyline caffeine clomipramine clozapine cyclobenzaprine estradiol fluvoxamine haloperidol imipramine N-DeMe maxillette naproxen olanzapine ondansetron phenacetin acetaminophen propranolol riluzole ropivacaine tacrine theophylline tizanidine verapamil (R)warfarin zileuton zolmitriptan	NSAIDs: diclofenac ibuprofen lornoxicam meloxicam S-naproxen_Nor piroxicam suprofen Oral Hypoglycemic: tolbutamide glipizide Angiotensin II Blockers: losartan irbesartan Sulfonylureas: glyburide glibenclamide glipizide glimepiride tolbutamide amitriptyline celecoxib fluoxetine fluvastatin glyburide nateglinide phenytoin-4-OH2 rosiglitazone tamoxifen tosemide S-warfarin	Macrolide antibiotics: clarithromycin erythromycin telithromycin Anti-arrhythmics: quinidine_3OH Benzodiazepines: alprazolam diazepam_3OH midazolam triazolam Immune Modulators: cyclosporine tacrolimus (FK506) HIV Antivirals: indinavir nelfinavir ritonavir saquinavir Prokinetic: cisapride Antihistamines: astemizole chlorpheniramine terfenadine Calcium Channel Blockers: amlodipine diltiazem felodipine lercanidipine nifedipine2 nisoldipine nitrendipine verapamil

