Appendix 10: Impact of Vemurafenib on Concomitant Medications (Cont.)

CYP 1A2 ¹	CYP 2C9 ¹	CYP3A4 ²
		
HMG CoA Reductase Inhibitors: atorvastatin cerivastatin lovastatin simvastatin
 
Steroid 6beta-OH: estradiol hydrocortisone progesterone testosterone
 
Miscellaneous: alfentanyl aprepitant aripiprazole buspirone cafergot caffeine cilostazol cocaine codeine-Ndemethylation dapsone dexamethasone dextromethorphan docetaxel domperidone eplerenone fentanyl finasteride gleeevec haloperidol irinotecan lidocaine melhadone nateglinide ondansetron pimoziide propranolol quetiapine quinine risperidone salmeterol

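### Inclusion criterion 11 accepts the pill or a hormone implant as sole contraception, although the protocol reports about 2-fold CYP3A4 induction by vemurafenib and lists progesterone as a CYP3A4 substrate whose exposure may fall

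*Combined protocol and SAP*

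**What the plan says.** **Eligibility.** Section 4.2, item 11, asks women of childbearing potential, and men with partners of childbearing potential, to use effective contraception throughout the study and for at least 6 months afterwards. It then lists what counts: "Effective forms of contraception includes surgical sterilization, a reliable barrier method with spermicide, birth control pills, or contraceptive hormone implants". The alternatives are joined by *or*, and no second method is required. Section 4.4.1 and the matching synopsis sentence tell oral contraceptive users to carry on and refer them back to the eligibility criteria.

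**Interaction.** Section 4.4.3 states that, in a study in patients, "vemurafenib inhibited CYP1A2 and induced CYP3A4 activity in melanoma patients by approximately 3-fold and 2-fold, respectively". If a CYP3A4 substrate has to be given, "investigators should monitor the signs of reduced benefit of CYP3A4 metabolized drugs due to a potential decrease in their plasma concentration". The same paragraph allows the dose of the other drug, though not of vemurafenib, to be changed where needed. Section 3.5 is softer: earlier data "suggest that the drug may be a mild inducer of CYP3A4".

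**Substrate list.** Section 4.4.3 says that Appendix 10 "includes a non-exhaustive list of typical examples of CYP1A2, CYP3A4, and CYP2C9 substrates". The CYP3A4 column contains "estradiol hydrocortisone progesterone testosterone", with a footnote that exposure may decrease. Estradiol also stands in the CYP1A2 column ("cyclobenzaprine estradiol fluvoxamine"), whose footnote says exposure may increase.

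**Fetal risk.** Section 3.10.2.2 reports that cobimetinib was teratogenic in rats at exposures like those of patients on 60 mg. Section 3.10.1 includes embryo-fetal toxicity among the safety events for vemurafenib. Under section 4.5, pregnancy ends study treatment.

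**The concern.** The eligibility section and the interaction section do not fit together. One treats a hormonal method as sufficient on its own. The other gives reason to think that vemurafenib could lower exposure to at least one hormone of the relevant class. A woman who complies fully could take two drugs with stated embryo-fetal risk while relying on a method that the same document calls into question.

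What is at stake is patient safety, not an estimate or an error rate. A pregnancy would expose a fetus to both drugs and end the patient's treatment.

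**Working it through.** There is no figure in the plan to reproduce on this point. The check sets the sections side by side, then does some arithmetic on duration and numbers.

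**1. Is a hormonal method alone enough under the text?** Yes. Item 11 accepts any one listed form, and sections 4.4.1 and the synopsis add nothing. No section of the protocol supplied requires a back-up method.

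**2. Does the protocol give a reason to doubt that method?** Yes, by inference.
- Induction of about 2-fold was measured in patients (4.4.3). The weaker wording in 3.5 does not contradict it.
- Progesterone appears only in the CYP3A4 column, so the documents give it one direction: down.
- Estradiol appears under CYP3A4 (down) and CYP1A2 (up), so its net direction is unclear. The point rests on progesterone.
- Section 1.3.5 says cobimetinib does not alter midazolam, a sensitive CYP3A substrate. Nothing suggests that it offsets the induction.

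**3. How large is the loss?** The documents do not say. As an illustration only, suppose CYP3A4 accounts for a share *f* of a hormone's clearance and CYP3A4 activity doubles. The exposure ratio is then 1/(1 + *f*):

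| *f* (assumed) | exposure ratio | fall |
|---|---|---|
| 0.25 | 0.80 | 20% |
| 0.50 | 0.67 | 33% |
| 0.75 | 0.57 | 43% |
| 1.00 | 0.50 | 50% |

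The value of *f* for any contraceptive hormone is not given, and neither is the link from exposure to contraceptive failure. The table shows only that the size is open.

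**4. Do the existing safeguards close the gap?**
- Monitoring for reduced benefit: the evident sign of a failed contraceptive is a pregnancy.
- Dose adjustment: no instruction covers contraceptives, and they are not among the medicines 4.4.3 names for discussion with a physician.
- Pregnancy testing: required at screening, then per local practice (Table 9, footnote 9). It detects a pregnancy; it does not prevent one.

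**5. How long after vemurafenib?** Section 1.2.2 states: "The mean effective half-life of vemurafenib across all dose cohorts was ~50 hours", with a range of 30 to 80 hours. Five half-lives leave 1/2^5 = 3.1% of the drug.
- 5 × 30 / 24 = 6.3 days
- 5 × 50 / 24 = 10.4 days
- 5 × 80 / 24 = 16.7 days

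A 28-day period would leave 28 − 16.7 = 11.3 to 28 − 6.3 = 21.7 days for enzyme activity to recover. The half-life describes drug elimination only; recovery time is not in the documents.

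**6. Who is in scope?** Section 8.3 expects about 130 combination patients plus up to 20 on monotherapy, so 130 + 20 = 150 planned. Sections 3.2 and 3.12 allow further expansion cohorts and extra patients in cleared cohorts, so 150 is not a ceiling. Only women of childbearing potential who use a hormonal method alone are affected, and their number is not given.

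Exposure to vemurafenib decides who is at risk, not the arm. Under 3.1.6 a patient may stop vemurafenib and stay on cobimetinib. Women in the monotherapy cohort are vemurafenib progressors (Table 5) who take vemurafenib through screening (5.3.1; Table 9, footnote 13), so some induction may carry over into their first weeks on cobimetinib.

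**The case against.** The strongest case against has four parts.

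- **The decisive step is not in the documents.** Appendix 10 names no contraceptive product. Going from progesterone to the pill or an implant requires knowing which hormones those products contain, how they are cleared and how much exposure they can lose. This stands: the text shows a missing precaution, not a method that has been shown to fail.
- **An investigator already has grounds to act.** Item 11 demands contraception that is effective at all times, and 4.4.3 permits dose changes for CYP3A4 drugs. In part this stands. But an investigator would have to connect three separate sections unaided, against a list that expressly accepts the pill and the implant.
- **Unseen sources may cover it.** Section 4.4.3 refers readers to a fuller online list and to the Investigator's Brochure, and the consent form was not available for review. A warning there cannot be ruled out. It would still leave the criterion itself at odds with that warning.
- **It is late.** This is Version L, a clinical study report has been written (section 18), and DSMB review has stopped (section 10). Few women may now be affected. That bears on how many benefit, not on whether the text is consistent. Version L still revises dose-modification rules, which suggests that some patients may remain on treatment.

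**Conclusion.** The point holds as an inconsistency worth correcting: a hormonal method is accepted alone, while the protocol's own interaction data give reason to doubt it and its safeguards act too late. It rests on the reported induction of about 2-fold, on progesterone being listed under CYP3A4 only, and on the inference that contraceptive hormones may behave in the same way.

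Three stronger readings are tempting and are not supported.

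- A reader might infer that the protocol shows the pill or implant to be ineffective with vemurafenib. It does not. The loss is inferred, its size is unknown, and estradiol points both ways.
- A reader might infer that the half-life limits how long the interaction lasts. It covers drug elimination only (about 6 to 17 days for five half-lives); enzyme recovery comes on top and is not documented.
- A reader might infer that the 6-month duty in item 11 should become a 6-month non-hormonal rule. Six months (182.5 days) is 182.5 / 16.7 = 11 to 182.5 / 6.25 = 29 times five half-lives. The interaction gives no reason for a rule of that length, and the general duty can stay as it is.

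**What to change.** In item 11 of section 4.2, in section 4.4.1 and in the matching synopsis sentence, state in substance:

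> For women of childbearing potential, a hormonal method alone is not sufficient while taking vemurafenib and for [period] after its last dose. A non-hormonal method, for example a barrier with spermicide, must be added to the hormonal method and not substituted for it.

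- Take the period from the Investigator's Brochure. About 4 weeks is a reasonable working assumption until that is checked.
- Count it from the last vemurafenib dose. This covers women who continue on cobimetinib alone and monotherapy-cohort women who have just stopped vemurafenib.
- Keep the general 6-month duty, and leave the list unchanged for partners of male patients, who do not take vemurafenib.
- Ask sites to identify women who now rely only on a hormonal method, and check that the consent text agrees.

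The cost is wording in three places, a consent check and a site notice. The downside is the small burden of a second method for women now using only a hormonal one. Sample size, visits and analyses do not change.

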4.3 Exclusion Criteria

A patient will be excluded if the answer to any of the following statements is "yes."

Cancer-Related Exclusion Criteria:

1. History of prior significant toxicity from another RAF or MEK pathway inhibitor requiring discontinuation of treatment
2. Allergy or hypersensitivity to components of the cobimetinib or vemurafenib formulations
3. Palliative radiotherapy within 2 weeks prior to first dose of study drug treatment in Cycle 1, Day 1
4. Experimental therapy within 4 weeks prior to first dose of study drug treatment in Cycle 1, Day 1 except vemurafenib
5. Major surgical procedure or significant traumatic injury within 14 days prior to first dose of study drug treatment in Cycle 1, Day 1 or anticipation of the need for major surgery during the course of study treatment
6.
 - a) For patients who participated in an antecedent vemurafenib study or progressed while receiving vemurafenib in a postmarketing setting: administration of any systemic anti-melanoma therapy other than vemurafenib during the interval between documentation of progression coincident with their vemurafenib exposure and consideration for this study will render the patient ineligible.
 - b) For previously untreated patients: no prior systemic, anti-cancer therapy (e.g., biologic or other targeted therapy, chemotherapy or hormonal therapy) for unresectable, locally advanced or metastatic melanoma disease. Note: Prior treatment in the adjuvant setting for previously resected melanoma is allowed.
 - c) For previously treated patients: no prior exposure to any BRAF or MEK inhibitor therapy; prior treatment with systemic chemotherapy or ipilimumab is allowed.
7. Active malignancy other than melanoma that could potentially interfere with interpretation of the PD or efficacy measures

Exclusion Criteria Based on Organ Function

Ocular:

8. Evidence of visible retinal pathology, as assessed by ophthalmologic examination, that is considered a risk factor for retinal vein thrombosis
9. Intraocular pressure > 21 mm Hg as measured by tonometry
10. History of RVO
11. Predisposing factors to RVO, including uncontrolled hypertension (Grade ≥ 2 at screening), uncontrolled diabetes (e.g., untreated or inadequately treated Grade ≥ 2 glucose intolerance), uncontrolled hyperlipidemia (e.g., untreated or inadequately treated Grade ≥ 2 hypercholesterolemia or hypertriglyceridemia) or hypercoagulable state

Cardiac:

12. History of clinically significant cardiac or pulmonary dysfunction, including the following:
 - Grade ≥ 2 hypertension (treated or untreated) or unstable angina
 - Current Grade ≥ 2 dyspnea or hypoxia or need for supplemental oxygen
 - History of symptomatic congestive heart failure of New York Heart Association \geq Class II (see [Appendix 4](#)) or serious cardiac arrhythmia requiring treatment, with the exceptions of atrial fibrillation and paroxysmal supraventricular tachycardia
 - History of myocardial infarction within 6 months prior to first dose of study drug treatment in Cycle 1
 - Current dyspnea at rest due to complications of advanced malignancy or any requirement for supplemental oxygen to perform activities of daily living
 - History of congenital long QT syndrome or QTc > 450 msec.

Central Nervous System:

13. Patients with active CNS lesions are excluded (i.e., those with radiographically unstable, symptomatic lesions). However, patients treated with stereotactic therapy or surgery are eligible if they remain without evidence of disease progression in the brain for ≥ 3 weeks. Whole brain radiotherapy is not allowed with the exception of patients who have had definitive resection or stereotactic therapy of all radiologically detectable parenchymal brain lesions.

General Exclusion Criteria:

14. The patient has not recovered to Grade ≤ 1 from adverse events due to investigational or other agents administered more than 28 days prior to enrollment except for alopecia.
15. Current severe, uncontrolled systemic disease (e.g., clinically significant cardiovascular, pulmonary or metabolic disease)
16. Inability or unwillingness to swallow pills

17. History of malabsorption or other condition that would interfere with enteral absorption of study drug
18. History of clinically significant liver disease (including cirrhosis), current alcohol abuse, or known infection with HIV, hepatitis B virus, or hepatitis C virus
19. Any condition requiring therapeutic anticoagulation (e.g., for chronic atrial fibrillation) with either warfarin, or unfractionated heparin. Note: Patients receiving anticoagulation with low-molecular weight heparin, and low-dose aspirin are eligible, as long as INR and aPTT are $\leq 1.5X$ ULN
20. Use of thrombolytics to establish patency of obstructed indwelling venous catheters is allowed.
21. Prophylactic anticoagulation to maintain patency of venous access devices is allowed as long as INR and aPTT are $\leq 1.5 X$ ULN.
